APPENDIX 2. PHARMACOKINETIC, BIOMARKER, IMMUNOGENICITY AND GENOMICS SAMPLING

Timepoint ^a	PK ^g (Plasma)	Biomarkers ^{b,f} (Serum and plasma)	CTGF ^b (Plasma)	HAHA/HAHA-NA ^e (Plasma)	Genomics ^{b,g} (Whole blood)	Tryptase (serum)
Day 1	X ^c	X	X	X ^b	X	
Day 8	X ^d					
Day 15	X ^d					
Week 3	X ^c					
Week 12	X ^c					
Week 24	X ^c	X	X	X ^b		
Week 36	X ^c		X	X ^b		
Week 48 /Last dose/ET	X ^c	X	X ^e	X ^b		
28 days after Last dose	X ^d	X	X ^f	X ^b		
Suspected Hypersensitivity/ Anaphylactic Reaction	X ^h		X ^h	X ^h		X ^h

Abbreviations: PK = Pharmacokinetic; CTGF = connective tissue growth factor; HAHA = human anti-human antibody; HAHA-NA = human anti-human antibody neutralizing antibody; ET = Early Termination

a.) For all time points, the actual date and time of sample collection must be recorded, in addition to date and time of study treatment administration.

b.) Sample should be collected within 2 hours prior to dosing start.

c.) Both pre-dose and post-dose samples are required for PK. Pre-dose sample collection should be within 2 hours prior to dosing and post-dose should be between 1-4 hours after dosing end.

d.) Only one sample is required. A ± 2 day window may be applied to the Day 8 and 15 sample.

e.) Samples with positive HAHA results will be tested for neutralizing antibody (HAHA-NA).

f.) Biomarkers will be collected in countries where the Regulatory Agencies allow collection of these samples.

g.) PK and DNA samples will be collected for subjects who consent, except in countries where the Regulatory Agencies do not allow collection of these samples

h.) In the event of a suspected hypersensitivity/anaphylactic reaction, PK, HAHA, HAHA-NA, CTGF and tryptase samples should be collected. The Tryptase sample should be drawn within 1 to 6 hours of immunogenic reaction, and all other samples should be collected within 24 hours of the immunogenic reaction.

APPENDIX 3. HRCT CRITERIA AND HISTOPATHOLOGICAL CRITERIA FOR UIP PATTERN

HRCT Criteria for UIP Pattern

UIP Pattern

- Subpleural and basal predominant; distribution is often heterogeneous¹
- Honeycombing with or without peripheral traction bronchiectasis or bronchiolectasis²

Probable UIP Pattern

- Subpleural and basal predominant; distribution is often heterogeneous
- Reticular pattern with peripheral traction bronchiectasis or bronchiolectasis
- May have mild ground-glass opacities (GGO)

Indeterminate for UIP

- Subpleural and basal predominant• Subtle reticulation; may have mild GGO or distortion (“early UIP pattern”)
- CT features and/or distribution of lung fibrosis that do not suggest any specific etiology (“truly indeterminate for UIP”)

Histopathological Criteria for UIP Pattern

UIP Pattern

- Dense fibrosis with architectural distortion (i.e., destructive scarring and/or honeycombing)
- Predominant subpleural and/or paraseptal distribution of fibrosis
- Patchy involvement of lung parenchyma by fibrosis
- Fibroblast foci
- Absence of features to suggest an alternate diagnosis

Probable UIP Pattern

- Some histologic features from column 1 are present but to an extent that precludes a definite diagnosis of UIP/IPF AND
- Absence of features to suggest an alternative diagnosis OR
- Honeycombing only

Indeterminate for UIP Pattern

- Fibrosis with or without architectural distortion, with features favoring either a pattern other than UIP or features favoring UIP secondary to another cause³
- Some histologic features from column 1, but with other features suggesting an alternative diagnosis⁴

¹ Variants of distribution: occasionally diffuse, may be asymmetrical.

² Superimposed CT features: mild GGO, reticular pattern, pulmonary ossification.

³ Granulomas, hyaline membranes (other than when associated with acute exacerbation of IPF, which may be the presenting manifestation in some patients), prominent airway-centered changes, areas of interstitial inflammation lacking associated fibrosis, marked chronic fibrous pleuritis, organizing pneumonia. Such features may not be overt or easily seen to the untrained eye and often need to be specifically sought.

⁴ Features that should raise concerns about the likelihood of an alternative diagnosis include a cellular inflammatory infiltrate away from areas of honeycombing, prominent lymphoid hyperplasia including secondary germinal centers, and a distinctly bronchiolocentric distribution that could include extensive peribronchiolar metaplasia.

APPENDIX 4. RADIATION RISK ASSESSMENT

The estimated radiation dose that results from participation in this study is based on an estimate is for a “standard patient” such as the MIRD phantom used in the ImPACT dose calculator spreadsheet. However, the ImPACT spreadsheet does not have a model for all CT platforms and for these the DLP*k method is used. For this method we assume a “standard sized” patient model, scan length is 25 cm (the length of the lungs for the MIRD Phantom) and a k factor of 0.014 mSv/mGy*cm for a thoracic scan (AAPM report 96 and European Guidelines 2000). For this study the expected doses are summarized in the table below.

Please NOTE that for each visit, one CT exam will be performed. That exam will consist of a required scan per imaging manual. Effective dose estimates provided: (For this study, visits occur at Baseline, Week 24 and Week 48 (i.e. 3 visits). Early Term scan is not required if a previous scan was completed within 4 months (excluding screening visit) of the ET visit.

Summary	
TLC scan – CTDIvol	6.1 mGy
TLC scan – DLP (25 cm scan)	153 mGy*cm
TLC scan only – DLP	153 mGy*cm
Effective Dose per CT exam (TLC only)	2.14 mSv per exam
Effective Dose per year (TLC only) (assume 2 studies each calendar year)	4.28 mSv per year
Effective Dose over entire study (TLC only) (3 studies)	6.42 mSv over entire study

For a comparison, the average annual exposure from background radiation (excluding medical exposure to population):

Based on National Average:	
United States	3.0 mSv per year
Canada	1.8 mSv per year
United Kingdom	2.5 mSv per year
Australia	2.0 mSv per year
Germany	2.0 mSv per year
India	2-2.5 mSv per year

References:

ImPACT <http://www.impactscan.org/ctdosimetry.htm>

AAPM - American Association of Physicists in Medicine (2008). The measurement, Reporting and Management of Radiation Dose in CT. Report No. 96 of AAP M Task Group 23, (2008)

European Commission (2000). European guidelines on quality criteria for computed tomography. EUR 16262 EN. Luxembourg, Office for Official Publications of the European Communities.

U.S. NRC Fact Sheet on Biological Effects of Radiation

APPENDIX 5. GAP SCORE CALCULATION

NOTE: For the screening FVC_{pp} value and GAP score calculation: the quality-controlled, Best-Test Review (BTR) assessment provided by the spirometry vendor over-reader, which is provided to sites within 48 hours after uploading the test, is to be used for eligibility assessment and GAP score calculation.

Use the FVC_{pp} and DLCO_{pp} that qualifies the subject for the study entry during screening
<https://www.mdcalc.com/gap-index-idiopathic-pulmonary-fibrosis-ipf-mortality>

		Points
Gender	Female	0
	Male	1
Age	≤ 60 years	0
	61-65 years	1
	> 65 years	2
Predicted Forced Vital Capacity (FVC _{pp})	> 75%	0
	50-75%	1
	< 50%	2
Predicted Diffusing Capacity of the Lung for Carbon Monoxide (DLCO _{pp})	> 55%	0
	36-55%	1
	≤ 35%	2
	Unable to perform	3
Total possible points		8

GAP STAGE CALCULATION

(GAP Stage is derived from the GAP Score taken during screening)

Stage	Points
Stage I	0-3
Stage II	4-5
Stage III	6-8

APPENDIX 6. OPTIONAL, OPEN LABEL EXTENSION (OLE) PHASE OF PAMREVLUMAB

Objective:

The objective of this open-label extension (OLE) phase is to evaluate the long-term safety of pamrevlumab in subjects with idiopathic pulmonary fibrosis (IPF).

This is an optional, open-label, single arm extension phase to provide continued access to pamrevlumab in subjects with IPF who completed the Week 48 visit of the main study and wish to participate in this OLE.

Efficacy Assessment:

The following efficacy assessments will be collected only as standard-of-care per each investigational site's real world practice and descriptively presented during the OLE period:

- FVC (L)
- FVC percent predicted (pp)
- Absolute FVC_{pp} decline of $\geq 10\%$
- All-cause mortality
- Respiratory hospitalizations
- Acute IPF exacerbations
- Change in HRCT Quantitative Lung Fibrosis (QLF) volume (if HRCT is performed as part of routine patient care)

Safety Assessments:

Treatment-emergent adverse events (TEAEs) and treatment-emergent serious adverse events (TESAEs; including hypersensitivity/anaphylactic reactions) will be collected for 60 days after the last dose.

In addition, pre- and post-infusion vital signs and immunogenicity (Human Anti-Human Antibody [HAHA] formation) testing will be collected.

Design

This is a multi-center, single-arm, open-label extension (OLE) phase in which subjects who complete the Week 48 visit of the main study are eligible to participate, as per Eligibility Assessments below.

All subjects will receive pamrevlumab in an open-label manner. **NOTE:** No unblinding of subject's treatment assignment in the main study will occur for purposes of OLE participation.

During the OLE treatment period, co-administration of an approved IPF therapy (i.e., pirfenidone or nintedanib) is acceptable if clinically indicated in the Investigator's opinion, provided that the Investigator assesses the potential risks/benefits of combining approved IPF therapies with pamrevlumab. See also Section 5.1.10 of the main study for details.

Eligibility Assessments:

All subjects participating in the OLE phase must have completed the Week 48 visit of the main study. In addition, the Investigator must consider the subject to be suitable for continued participation in this phase, including ability to comply with study visits every 3 weeks for pamrevlumab infusions.

A signed and dated IRB/IEC-approved informed consent must be obtained before dosing start, and preferably on or before the Week 48 visit of the main study.

Male subjects with partners of childbearing potential and female subjects of childbearing potential (including those <1 year postmenopausal) must continue to use highly effective contraception methods (per Section 5.2.3) until 3 months after the last dose of study drug in the OLE phase.

Additional consideration for participation in the OLE

The following conditions are excluded for continued participation in this OLE phase:

- Female subjects who are pregnant or nursing.
- Use of any investigational drugs, or participation in a clinical trial with an investigational new drug, other than participation in the main study.
- History of allergic or anaphylactic reaction to human, humanized, chimeric or murine monoclonal antibodies, or experienced an allergic or anaphylactic reaction to study drug or to any component of the excipient while participating in the main study.
- Subjects who withdrew informed consent while participating in the main study.
- The Investigator judges that the subject is not suitable for participation, or is unable to fully participate in the OLE phase and complete it for any reason, including inability to comply with study procedures and treatment, or any other relevant medical or psychiatric conditions

Study Duration

The OLE phase will end either after the last subject completes 48 weeks of treatment, or pamrevlumab is commercially for the indication of IPF, or the Sponsor decides to end the OLE phase, whichever occurs first.

Subjects may withdraw from the OLE at any time, for any reason. Such subjects will have an early termination visit (EX ET) as soon as feasible. Study procedures to be performed during the EX ET visit can be found in the OLE Schedule of Assessments (SOA) presented in Appendix 6. Also these subjects will have a Safety Follow-Up Visit 28 days after the last dose and a final follow-up safety phone call 60 days after the last dose.

Any assessments repeated as a part of main study, and all AEs prior to first dose in OLE are considered part of the main study.

Study Drug Dosing instructions and Visit Schedule

Each subject will receive pamrevlumab (30 mg/kg) every 3 weeks, using the weight obtained on Day 1 of the OLE phase (=EX Day 1), and every 24 weeks thereafter, for assessment of the proper weight-based dosing regimen. EX Day 1 is expected to be scheduled 3 weeks \pm 7 days after the Week 48 visit of the main study.

See Protocol Section 5 for detailed information on study drug infusions. Home infusions via home health care (HHC) may be available during the OLE phase of the study at the discretion of the Investigator but such home infusions services will not be reimbursed by the Sponsor. Any home infusions via home health care are not permitted until at least three infusions in the OLE period have been administered without safety concerns.

Subjects who experience a significant infusion-associated AE may not receive HHC. In addition, if a new safety concern arises during a home infusion, the subject has to attend an on-site visit for an Investigator assessment as soon as feasible.

Medications and supplies to treat suspected hypersensitivity/anaphylactic reactions must be available for immediate use for all study drug infusion visits.

Important NOTE: The infusion durations and post-infusion observations periods have to be followed per Table 1 in Protocol Section 5.1.6, including the initial dosing and observations periods. This is to ensure that subjects transitioning from placebo (in the double blinded phase) receive adequate safety monitoring during OLE.

Visit windows are within ± 7 days of the scheduled visit date from OLE (EX) Week 3 through last dose in the OLE; however, visits should be at least 10 days apart, to ensure intervals of at least 10 days between study drug infusions.

All study visits will be performed in accordance with the OLE Schedule of Assessments (SOA) presented in Appendix 6.

Missed Visits/Missed Doses

Scheduled visit dates are determined from the time of the first dose in OLE, which is defined as EX Day 1. If a subject misses a visit, the subject should resume the regular visit schedule at the next scheduled visit.

Missed doses are not to be made up through extra visits. If a subject misses more than two infusions in any 18-week period, or two sequential infusions, the FibroGen Medical Monitor should be notified. The reason for missed doses must be documented in the subject's clinical record.

NOTE: In accordance with FDA/EMA Guidance: During the COVID-19 pandemic, the visit modality (e.g.: in-person versus remotely) and scheduling maybe adjusted and conducted at the discretion of the Investigator, in accordance with the site's rules and recommendations, and using all necessary precautions. If a visit has to be done remotely, it can be conducted with any technology available to the site and study subjects.

Unscheduled Visits

Unscheduled visits/assessments will be captured accordingly in the clinical database

Subject Study Withdrawal Criteria

Subjects may withdraw from the OLE at any time, for any reason. Such subjects will have an early termination visit (EX ET) as soon as feasible. Study procedures to be performed during the EX ET visit can be found in the OLE Schedule of Assessments (SOA) presented in Appendix 6. Reasons for withdrawal will be captured on CRF.

Mandatory reasons for withdrawing from the OLE phase include:

- Any safety concern in the Investigator's opinion, that precludes further study participation
- Lung transplant
- Pregnancy
- Withdrawal of Consent

Safety Follow-Up

All subjects will have two Safety Follow-Up Visits:

- 28 days after the last dose
- 60 days after last dose: follow-up phone call, for a final safety assessment

The visit windows for the safety assessments are: 28 days +7 days and 60 days +7 days (phone call) after the last dose.

See OLE SOA in Appendix 6.

After the protocol-required reporting period (60 days after the last dose), the Investigator does not need to actively monitor subjects for SAEs. However, if the Investigator becomes aware of an SAE/death that may be possibly related to study treatment after the protocol-required reporting period, the Investigator may report the event to FibroGen as outlined in Section 7 of the main study. SAEs reported outside of the protocol-required reporting period will be captured within the safety database only as clinical trial cases for the purposes of expedited reporting.

Study Assessments:

All study assessments are done per the local standard of care with the exception of weight, pre and post infusion vital signs and pregnancy test. Refer to OLE SOA for details.

Vital Signs (including Weight) – Pre and Post pamrevlumab infusion

Vital signs to be collected include heart rate, blood pressure and temperature:

- Heart rate should be collected as beats/min
- Systolic and diastolic blood pressure should be collected from subjects in seated position (mmHg)
- Temperature should be taken as oral or tympanic and captured as °F or °C

Weight is collected at EX Day 1 and every 24 weeks thereafter for purposes of adjusting the weight-based dose if necessary.

Laboratory Evaluations

Local lab results, done as part of local standard-of-care, will not be recorded on CRF; local lab results will be reviewed by the Investigator for clinical significance and to determine appropriate reporting of adverse events (see Section 7.3.7 of the main study).

Pregnancy tests (performed pre-dose EX Day 1, and at other study visits) apply only for women of childbearing potential (WOCBP). Urine pregnancy test should be done by the site using site supplies. A positive urine pregnancy test must be confirmed by serum hCG using the site local labs for testing. At 60 days after last dose, a urine pregnancy test to be done at home by the

subject (WOCBP) and report result to site. In each case of delayed menstrual period (over one month between menstruations) confirmation of absence of pregnancy is strongly recommended. This recommendation also applies to WOCBP with infrequent or irregular menstrual cycles.

PFTs and HRCT

PFTs and HRCTs are performed locally, and at a frequency according to local SOC, as determined by the Investigator. These tests will not be reimbursed by Sponsor.

All local spirometry results are entered into EDC.

If HRCT scans are done, they should be uploaded to the same Independent Radiology Review Group as for the main study.

Human Anti-Human Antibodies (HAHA)

Plasma samples will be collected for evaluation of human anti-human antibodies (HAHA), in all subjects participating in the OLE at the 28 days after last dose Safety Follow-Up Visit. A specialty laboratory will measure HAHA titers using a validated assay.

Samples with positive HAHA results will be tested for neutralizing antibody (HAHA-NA). The prevalence and duration of binding and neutralizing antibodies and the effect of these antibodies on the pharmacokinetics, pharmacodynamics markers, efficacy, and safety of pamrevlumab will be assessed.

Suspected Hypersensitivity or Anaphylactic Reactions

Any immunogenic reactions, including drug-related hypersensitivity or anaphylaxis, should have PK, HAHA, HAHA-NA, CTGF and tryptase drawn within 24 hours of a suspected reaction from pamrevlumab (see **OLE PHARMACOKINETIC, CTGF AND IMMUNOGENICITY SAMPLING SCHEDULE OF ASSESSMENTS** for more detail).

This will not be considered optional for the subject unless there is local institutional guideline consideration for total blood volume collection on the same day as a standard blood draw timepoint, which could preclude the subject from having this collection take place within 24 hours. The Tryptase sample should be drawn within 1 to 6 hours of immunogenic reaction, and all other samples should be collected within 24 hours of the immunogenic reaction. See **OLE PHARMACOKINETIC, CTGF AND IMMUNOGENICITY SAMPLING SCHEDULE OF ASSESSMENTS** for more detail.

Statistical Considerations:

Data collected during the extension period will be summarized descriptively.

OLE Schedule of Assessments

Study Week	Dosing Period ^{a, b}			Follow-Up Period ^o	
	EX-Day 1 ^c	Q3 Weeks	Q24 ^o Weeks /Last dose/EX ET ^p	28 days after Last dose ⁿ	60 days (phone call) after Last dose ⁿ
Assessment					
Weight	X ^d		X ^d		
Vital Signs ^e	X	X	X	X	
Infusions ^e	X	X	X ^q		
AEs/SAEs ^f	X	X	X	X	X
Concomitant Medications ^g	X	X	X	X	X ^g
Procedures and Nondrug Therapies ^g	X	X	X	X	X ^g
PFTs (local) ^{h, i, j}	SOC		SOC		
Labs (local) ^{h, i, k}	SOC		SOC	SOC	
HRCT of Chest ^{i, l}	SOC		SOC		
Pregnancy Test (urine) (WOCBP) ^m	X	X	X	X	X ^m

Abbreviations: AE = adverse event; SAE = serious adverse event; hCG = human chorionic gonadotropin; HRCT = high resolution computed tomography; PFTs = Pulmonary Function Test; (SOC) = not required at time-points noted above, but assessed per timing of local standard of care; EX = Extension; WOCBP = Woman of child bearing potential; HAHA = human anti-human antibody; HAHA-NA = human anti-human antibody neutralizing antibody EX ET = Extension Early Termination

- a.) EX Day 1 is expected to be scheduled 3 weeks ± 7 days after the Week 48 visit of the main study. Pamrevlumab is dosed Q3W starting with EX-Day 1. Visit windows of ± 7 days, EX Week 3 through Follow-Up Period. Missed visits are not to be made up between scheduled visits, subject is to return for the next scheduled visit
- b.) Unscheduled visit assessments (procedures) will be determined by the investigator. During the COVID-19 pandemic, the visit modality (e.g.: in-person versus remotely) and scheduling maybe adjusted and conducted at the discretion of the Investigator, in accordance with the site's rules and recommendations, and using all necessary precautions. If a visit has to be done remotely it can be conducted with any technology available to the site and study subjects.
- c.) Ensure subject has signed the informed consent at or before Week 48 visit of the main study and eligibility considerations have been assessed prior to EX Day 1 infusion.
- d.) Weight will be measured at EX Day 1 and every 24 weeks thereafter to determine dose for the subsequent 24-week interval.
- e.) Infusions must be at least 10 days apart. Vital signs (blood pressure, pulse, and temperature) must be recorded prior to, and after each infusion. The infusion durations and post-infusion observations periods have to be followed per Table 1 in Protocol Section 5.1.6, including the initial dosing and observations periods. Any home infusions via home health care are not permitted until at least three infusions in the OLE period have been administered without safety concerns. If a new safety concern arises during a home infusion, the subject has to attend an on-site visit for an Investigator assessment as soon as feasible.

- f.) See Section 7 of the main protocol for safety assessments.
- g.) Concomitant medications and nondrug therapies are recorded after signing of informed consent and ending 28 days after the last dose. If the subject experiences an AE or SAE before the end of the final safety phone call (60 days after last dose), concomitant medications and nondrug therapies may also be collected, if part of the treatment of the AE/SAE.
- h.) Local Labs and PFTs are performed pre-dose.
- i.) Collected according to local standard of care.
- j.) PFT will be done locally, and at a frequency per local SOC, and recorded on CRF whenever they are performed locally.
- k.) Labs will be done locally and at a frequency per local SOC. Lab data will NOT be recorded on CRF. Clinically significant laboratory abnormalities will be reported in the context of AE reporting; do not report non-clinically significant lab abnormalities as AE
- l.) HRCT scans will be performed at a frequency per local SOC. Any HRCT scan will be uploaded to central HRCT radiology vendor
- m.) Pregnancy tests (performed pre-dose EX Day 1, and at other study visits) only apply for WOCBP, and are to be performed via urine pregnancy test. A positive urine pregnancy test must be confirmed by serum hCG. At 60 days after last dose, a urine pregnancy test to be done at home by the subject (WOCBP) and report result to site. In each case of delayed menstrual period (over one month between menstruations) confirmation of absence of pregnancy is strongly recommended. This recommendation also applies to WOCBP with infrequent or irregular menstrual cycles.
- n.) Subjects should attend a Safety Follow-Up visit 28 days after the last dose. These subjects will also be contacted by phone for a Safety Follow-Up call at 60 days after the last dose for a final safety assessment. The visit window for safety follow up period are: 28 days + 7 days (visit) and 60 days + 7 days (phone call) after the last dose. If the subject experiences an SAE, it must be reported within 24 hours of awareness (see Section 7.3 for details).
- o.) The OLE phase will end either after the last subject completes 48 weeks of treatment, or pamrevlumab is commercially for the indication of IPF, or the Sponsor decides to end the OLE phase, whichever occurs first
- p.) Subjects who terminate / withdraw from the OLE phase for any reason, will have an Extension Early Study Termination (EX ET) visit as soon as feasible. IP infusion will not be done at the EX ET visit

OLE PHARMACOKINETIC, CTGF AND IMMUNOGENICITY SAMPLING SCHEDULE OF ASSESSMENTS

Timepoint	PK (Plasma)	CTGF (Plasma)	HAHA/HAHA-NA (Plasma)	Tryptase (serum)
28 days after Last Dose			X ^a	
Suspected Hypersensitivity/ Anaphylactic Reaction	X ^b	X ^b	X ^b	X ^b
Abbreviations: PK = Pharmacokinetic; CTGF = connective tissue growth factor; HAHA = human anti-human antibody; HAHA-NA = human anti-human antibody neutralizing antibody				

- a.) All subjects participating in the OLE will have a HAHA sample taken 28 days after the last dose. Samples with positive HAHA results will be tested for neutralizing antibody (HAHA -NA) assays and analyses
- b.) In the event of a suspected hypersensitivity/anaphylactic reaction, PK, HAHA, HAHA-NA, CTGF and tryptase samples should be collected. The Tryptase sample should be drawn within 1 to 6 hours of immunogenic reaction, and all other samples should be collected within 24 hours of the immunogenic reaction.

Signature Page for VV-CLIN-013474 v1.0

Approval Task	 14-Jan-2023 15:45:49 GMT+0000

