4.4. Subject Study Withdrawal Procedures/Assessments

Subjects who terminate / withdraw from the study early, for any reason, will have an Early Study Termination (ET) visit as soon as feasible. Study procedures to be performed during the ET visit can be found in the SOA (Appendix 1). At the ET visit, PFTs and questionnaires do not have to be repeated, if the last one (excluding screening visit) was performed within 8 weeks of this visit; HRCT does not have to be repeated, if the last one (excluding the screening visit) was performed within 4 months of this visit.

These subjects will have a safety follow-up visit 28 days after the last dose. A follow-up phone call 60 days after last dose will also be completed for a final assessment of safety.

In addition, these subjects should be contacted by phone for vital status at weeks 24 and 48. These subjects will not be eligible for the OLE phase.

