5.3. General Data Handling Rules and Presentation Specifications

5.3.1. Analysis Period

• The primary analysis will be based on the on-study period which is defined as from Day 1 in the OLE period up to the end of the entire study, regardless of patients' treatment status.

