6.6.1.3. Intercurrent Event Handling Strategy

Treatment policy strategy will be used for any intercurrent event. No imputation on missing data.

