APPENDIX 2. ANALYSIS OF ASSOCIATION BETWEEN QLF AND OS

Cox proportional hazard (PH) analyses on the association between QLF and overall survival (OS) will be performed for the ITT population including both double-blind and OLE periods. The hazard ratio and its corresponding 95% CI between QLF Test Group vs QLF Reference Group. A stratified log-rank test stratified by randomization stratification factor will be used for treatment comparison.

No imputation will be performed on missing data. On-treatment analysis will be optional.

- QLF as a predictor:
- 1. To investigate whether baseline QLF is a significant predictor of mortality, a Cox PH model will include electronic data capture (EDC) GAP stage (I/II/III), and prior IPF treatment (Yes/No) as covariates, baseline QLF% (cutoff such as 15%, 20%, or 25%) as the predictor variable.
- 2. Similar analysis on baseline QLF volume (ml) will be performed as in 1), using baseline QLF volume (ml) (cutoff such as 300ml, 400ml, and 500ml) as the predictor variable.
- 3. In addition, Cox PH model including EDC GAP stage (I/II/III), and prior IPF treatment (Yes/No) as covariates, baseline QLF% or QLF volume (ml) (as a continuous variable) as the predictor variable, will be performed.
 - Change from baseline in QLF at Week 24 as a predictor
- 1. In addition, to investigate the association between change from baseline in QLF% (baseline to Week 24) and OS, the Cox PH model will include EDC GAP stage (I/II/III), prior IPF treatment (Yes/No), and baseline QLF% (as a continuous variable) as covariates, and category in change from baseline in QLF% (e.g., ≥2% vs <2%) as the predictor variable.
- 2. Similar analysis on QLF volume (ml) change from baseline will be performed as in 4) with baseline QLF% replaced with baseline QLF volume as a continuous covariate, and change from baseline in QLF volume (ml) as the predictor variable with a cutoff (e.g., ≥40 mL vs <40mL) will be performed.

STATISTICAL ANALYSIS PLAN

TITLE PAGE

A Phase 3, Randomized, Double-Blind, Placebo-

STUDY TITLE: Controlled Efficacy and Safety Study of Pamrevlumab in

Subjects with Idiopathic Pulmonary Fibrosis (IPF)

PROTOCOL NUMBER: FGCL-3019-095 (ZEPHYRUS 2)

FibroGen, Inc.

STUDY SPONSOR: [name]

[name]

STUDY DRUG: Pamrevlumab

INDICATION: Idiopathic Pulmonary Fibrosis (IPF)

PROTOCOL VERSION: Version 2.0

SAP VERSION Final V1.0 (Double-Blind Period)

RELEASE DATE: 12Jun2023

CONFIDENTIALITY STATEMENT

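### In the OLE, vital status is not systematically collected beyond 60 days after the last dose, although all-cause mortality is an OLE outcome with an analysis window running to the end of the study

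*Protocol*

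**What the plan says.** **Outcome.** Protocol Appendix 6 (Efficacy Assessment) lists "All-cause mortality" among the OLE outcomes, to be collected as standard of care and presented descriptively. OLE SAP section 4 keeps it.

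**Window.** OLE SAP 5.3.1 bases the primary analysis on data "from Day 1 in the OLE period up to the end of the entire study, regardless of patients' treatment status". OLE SAP 6.6 applies this on-study period to all efficacy endpoints unless noted otherwise. Section 6.6.1.3 adds: "Treatment policy strategy will be used for any intercurrent event", with no imputation.

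**Collection.** A subject who leaves the OLE has an early termination visit, a visit 28 days after the last dose and "a final follow-up safety phone call 60 days after the last dose" (Appendix 6, Study Duration). The call has a +7-day window. For the time after that, Appendix 6 (Safety Follow-Up) says: "After the protocol-required reporting period (60 days after the last dose), the Investigator does not need to actively monitor subjects for SAEs". The OLE Schedule of Assessments has no vital-status row.

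**Main-study contrast.** For early withdrawals from the double-blind phase, Protocol 4.4 says "these subjects should be contacted by phone for vital status at weeks 24 and 48". Protocol 6.1.4 and Appendix 1 (footnote q) repeat this. Appendix 6 has no counterpart.

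**Second use of OLE survival.** OLE SAP Appendix 2 plans Cox models of QLF against overall survival that "will be performed for the ITT population including both double-blind and OLE periods".

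**The concern.** The analysis window asks for deaths to the end of the study, but the schedule supplies them only to about two months after each subject's last dose. Subjects still being dosed are seen every 3 weeks, so the gap concerns those who stop more than 60 days before the OLE closes. They may well be sicker than those who stay: Protocol 2.6.3 reports that IPF progression was the most frequent cause of treatment or study discontinuation in Study 049, and in the OLE a safety concern that precludes further participation is a mandatory withdrawal reason.

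Long-term safety is the stated objective of the OLE. A death count presented as running to study end, but in fact ending at day 60 for leavers, could make long-term mortality look more favourable than it is. The overall survival models in OLE SAP Appendix 2 would be censored at the same point.

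**Working it through.** **Step 1. Can another route fill the gap?** The protocol has three rules for a death after day 60.
- Appendix 6: an investigator who learns of a death possibly related to treatment may report it.
- Protocol 7.3.5.2: a death considered related is reported as an SAE.
- Appendix 6 and Protocol 7.3.5: such reports go to the safety database only and are left out of the clinical study report.

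Late deaths are therefore selected by awareness and by judged relatedness, and then excluded. They do not supply all-cause mortality.

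**Step 2. Which estimator applies?** The OLE SAP gives none for mortality. Sections 5.3.5 and 6.6.1.4 refer to the double-blind SAP, whose section 6.7.2.1.4.4 treats mortality as time-to-event, censored at the last date known alive. Both a crude proportion and a censored estimate are therefore examined.

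**Step 3. Illustration.** The documents give no OLE mortality or withdrawal figure, so there is nothing to reproduce and every input is an assumption:
- death hazard on OLE drug of 8-12% per year. The only anchor is Phase 2 Study 067 (Protocol 2.6.3): 3 of 50 = 6% on pamrevlumab and 6 of 53 = 11% on placebo;
- 15%, 25% or 35% leaving by day 336, at a constant rate;
- hazard after leaving k = 1, 2 or 4 times the hazard before;
- deaths recorded to 60 days after leaving.

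With death hazard λ, leaving hazard μ and T = 336 days:
- deaths before leaving: λ/(λ+μ) × [1 − e^(−(λ+μ)T)]
- deaths after leaving: ∫ μ e^(−(λ+μ)t) [1 − e^(−kλ(T−t))] dt, from 0 to T
- of those, recorded: the same integral with T−t replaced by min(T−t, 60)

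Example (12% per year, 25% leaving, k = 2): λ = 0.12/365.25 = 0.000329 per day and μ = −ln(0.75)/336 = 0.000856 per day. Deaths before leaving are 0.0911. Deaths after leaving are 0.0259, of which 0.0085 are recorded. The true risk is 0.0911 + 0.0259 = 0.1170, and the crude observed risk is 0.0911 + 0.0085 = 0.0996. The share missed is 0.0174/0.1170 = 15%.

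For the censored estimate, the hazard at time t is [λN + kλF]/[N + F]. N = e^(−(λ+μ)t) is the fraction still on drug, and F is the fraction alive who left within the past 60 days. The risk is 1 − exp(−∫ hazard dt).

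Results at 48 weeks, 25% leaving, 12% per year:

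| k | True | Crude | Missed by crude | Censored |
|---|---|---|---|---|
| 1 | 10.5% | 9.5% | 9% | 10.5% |
| 2 | 11.7% | 10.0% | 15% | 10.9% |
| 4 | 13.9% | 10.8% | 23% | 11.8% |

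At 8% per year the missed shares are 9%, 15% and 24%, so the mortality level hardly matters. Across 15-35% leaving, the range is about 5-31%. OLE SAP 6.5.1 has exposure categories beyond 96 weeks, so 48 weeks is the mild case: at 96 weeks the same model gives about 12-51%.

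**Step 4. Cross-check with other assumptions.** Take 48-week death risks of 6% and 11%, 10-30% stopping per 48 weeks and k = 1 to 3. The crude proportion misses 3-24% of deaths at 48 weeks and 8-43% at 96 weeks, and it is low in all 36 scenarios. The censored estimate equals the true risk whenever k = 1. With 11%, 20% stopping and k = 2, the 96-week true, crude and censored risks are 24.1%, 18.2% and 21.5%.

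**The case against.** Four points on the other side have force.

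1. A reader might infer that the OLE collects no survival information after day 60. That is too strong, because deaths thought related can still be reported. What is missing is systematic collection.

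2. A reader might infer that OLE mortality is understated. The documents do not establish this. They specify no crude proportion, and if the double-blind rule of censoring at last known alive carries over, leavers with unchanged hazard cause no bias. Informative leaving is a reasonable expectation, not a documented fact.

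3. A reader might take 6.6.1.3 as claiming a treatment-policy estimand for mortality. Yet 6.6.1.1 frames the estimand for a continuous endpoint, and 6.6.1.5 names FVC, FVCpp and the HRCT fibrosis score. Only the general window in 5.3.1, through 6.6, reaches mortality. That window also speaks of treatment status, not study withdrawal, and OLE SAP 3.3 ends the follow-up period with the 60-day call. One could therefore read it as ending at each subject's last contact. The wording "up to the end of the entire study, regardless of" treatment status does not say so, and this ambiguity is a reason to state the rule.

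4. The OLE is single-arm and descriptive, with no formal inference (OLE SAP 5.3.4). Confirmatory mortality is tested on double-blind data, supported by the vital-status calls.

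All four limit the point. None closes the gap between the outcome as defined and the data as scheduled. On Appendix 2, ITT subjects who never enter the OLE also have no survival contact scheduled after Week 48 and the safety follow-up, so that censoring problem is wider than the OLE.

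**Conclusion.** The mismatch holds on the text: mortality is an OLE outcome, its window runs to study end, and scheduled contact stops at 60 (+7) days after the last dose. Following the plan as written gives an incomplete death count for early leavers.

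The direction and size of any bias depend on an estimator and a leaving pattern that the documents do not give. The 9-24% range (5-31% across 15-35% leaving) is a share of deaths missed by a crude proportion under assumed inputs. It is not an estimate for this trial. Under censoring, the bias runs from nil (equal hazard) to a smaller shortfall than the crude one.

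No confirmatory conclusion changes. What is affected is the descriptive long-term mortality summary and, through censoring, the survival models in OLE SAP Appendix 2. The change is worth making because it is cheap and the sponsor already uses the procedure in the main study.

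**What to change.** **Preferred.** Add to Appendix 6 and the OLE Schedule of Assessments a vital-status contact at OLE close for every subject who left the OLE early and has not refused further contact. Count deaths and person-time to that contact. A single call at EX Week 48 would not match a window that runs to study end.

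**Otherwise.** Define the outcome in Appendix 6 and OLE SAP section 4 as deaths up to 60 days after the last OLE dose, end person-time or censor there, and exempt mortality from the end-of-study window in OLE SAP 5.3.1. The exposure-years formula in OLE SAP 5.3.3 stops at the last dose, so it would not be the matching denominator.

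**In either case,** name the mortality estimator and its censoring rule in the OLE SAP. State the overall survival censoring rule in its Appendix 2, including for subjects who never enter the OLE.

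**Cost.** The first option takes one phone call per early leaver: 25 calls per 100 OLE entrants if 25% leave. It cannot cover those who refuse contact. The second needs only wording, and its downside is a narrower stated outcome.
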